7.3 Secondary study parameter(s)

- Disability free survival will be described as percentages with their accompanying 95% confidence interval (CI) among patients with or without PMI. Different combinations of elevation in biomarkers will be tested. Comparison between different PMI phenotypes will be performed using chi-square test or Fisher's exact and multivariable logistic regression

analyses will be done to take several covariates into account, which are similar to confounders described for the primary analyses.

- Similar to disability free survival, MACE (including PMI and NITE), noncardiac MAPE and all-cause mortality will be presented as proportions with their accompanying 95% CI. Multivariable logistic regression analyses will be performed using MACE, noncardiac MAPE or all-cause mortality as outcomes, both in-hospital events and at 6 months (except for noncardiac MAPE as these will not be measured at 6 months). Different combinations of elevations in biomarkers (preoperative, postoperative and change between pre- and postoperative) will be tested against these outcomes to uncover correlations between particular combinations of elevated biomarkers to assess what disease entities are related to the outcome.
- A Kaplan-Meier method will be used to assess whether the cumulative incidence of 6-month mortality differs between patients with and without PMI. The probabilities of 6-month mortality between patients with and without elevation in (one or more) biomarker(s) will be compared using log-rank tests provided assumptions for this test are met. Cox-proportional hazard analyses will be performed to examine whether (one or a combination of several) biomarker(s) are associated with 6-month mortality adjusted for potential confounders.
- The added prognostic value of each of the biomarkers (or combinations of biomarkers) will be tested to predict MACE, both in-hospital and at 6-months. The biomarkers will be analyzed as continuous variables and using predefined clinical thresholds to define whether that particular biomarker is elevated. Multivariable logistic regression analyses will be performed using the predictors of the RCRI (i.e. high risk surgery, history of cerebrovascular disease, history of myocardial infarction, congestive heart failure, elevated creatinine and insulin dependent diabetes) as predictors together with the addition of elevation in biomarkers. Discrimination and calibration of the prediction models will be assessed using the c-statistic, Hosmer-Lemeshow test. The net reclassification index (NRI) and the Integrated Discrimination Index (IDI) will be calculated to quantify how well the updated RCRI reclassifies patients as compared to the traditional RCRI.

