beginning of the study, the estimated inclusion time is one year with six months follow-up resulting in a total study time of 18 months.

Main study parameters/endpoints:**Primary end points:**

Disability is expressed in terms of the WHODAS 2.0 which is based on different functional domains, including cognition, mobility, self-care, getting along, life activities and participation.

Secondary endpoints:

- *Disability free survival* is defined as being alive with a WHODAS 2.0 score $\leq 25\%$ and no increase of the preoperative score $\geq 25\%$ at 6 months after surgery.
- *An in-hospital major adverse postoperative events (MAPE)*, which could be distinguished in:
 - o *Major adverse cardiac event (MACE)*, which is defined as the composite endpoint of cardiovascular death, non-fatal myocardial infarction, non-fatal cardiac arrest, non-fatal ventricular fibrillation, non-fatal ventricular hemodynamic compromise and atrial fibrillation requiring cardioversion.
 - o *Noncardiac MAPE*, which is defined as a composite outcome consisting of respiratory disorders (including pneumonia and respiratory failure), pulmonary embolism, sepsis and/or systemic inflammatory response syndrome (SIRS), renal failure, reoperation and unplanned ICU admission.
- *In hospital all-cause mortality*
- *Length of hospital stay*
- *6-month MACE*
- *6-month all-cause mortality*

Nature and extent of the burden and risks associated with participation, benefit and group**relatedness:**

In addition to routine care, patients will be asked to fill out the WHODAS 2.0 before surgery and additional blood will be drawn (7 cc in total) before induction of anesthesia. Postoperatively, extra blood will be taken up to three days after surgery (7 cc in total each time) during routine blood draws. At postoperative day 2, an electrocardiogram (ECG) and transthoracic echo (TTE) will be performed. Six months after surgery, patients will be asked to fill out the WHODAS 2.0 for the second time and their GPs will be approached to assess whether clinically relevant events have occurred. The study is associated with a negligible risk as only noninvasive imaging procedures will be performed

and blood will be drawn. The treating physician will be notified in case any unexpected findings from the ECG and TTE are observed meaning that participation to this study could lead to early recognition of heart disease.

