5.1.2 Secondary study parameters/endpoints

- *Disability free survival* is defined as being alive with a WHODAS score $\leq 25\%$ and no increase of the pre-operative score $\geq 25\%$ at 6 months after surgery.
- *An in-hospital major adverse postoperative events (MAPE)*, which could be distinguished in:
 - o *Major adverse cardiovascular event (MACE)*, which is defined as the composite endpoint of:
 - Cardiovascular death, defined as death resulting from an acute myocardial infarction, sudden cardiac death, death due to heart failure, death due to stroke, and any acute death unconfirmed yet probably due to a cardiovascular cause.
 - Non-fatal myocardial infarction, defined in accordance to the third universal definition of myocardial infarction¹⁰.
 - Non-fatal cardiac arrest.
 - Non-fatal ventricular fibrillation.
 - Ventricular arrhythmia with hemodynamic compromise.
 - Atrial fibrillation requiring cardioversion.
 - Pulmonary embolism, defined as a new thrombus within the pulmonary arterial system confirmed on CTA
 - Stroke confirmed on CT.
 - o *Noncardiac MAPE*, which is a composite outcome consisting of:
 - Respiratory failure including pneumonia and hypoxia or hypercapnia leading to ICU admission for respiratory support

- Sepsis and/or systemic inflammatory response syndrome (SIRS), defined as life-threatening organ dysfunction caused by a dysregulated host response to infection²⁸.
- Renal failure, defined as AKIN criteria or renal replacement therapy.
- Unplanned ICU admission
- Unplanned medium care admission
- Reoperation
- *Length of hospital stay, defined as the number of days from the end of surgery until day of discharge*
- *In-hospital all-cause mortality*
- *6-month all-cause mortality*
- *6-month MACE*

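### Section 7.3 counts PMI and NITE as MACE, which no MACE list in the protocol does; if followed, most MACE events would be troponin elevations and would overlap with postoperative troponin as a predictor

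*Combined protocol and SAP*

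**What the plan says.** MACE is listed four times: twice in the summary (objectives; secondary endpoints), in section 2.2 and in section 5.1.2. None of these lists names PMI or NITE. The only myocardial-injury item is MI, in 5.1.2 as "Non-fatal myocardial infarction, defined in accordance to the third universal definition of myocardial infarction".

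Section 7.3 words it differently: "MACE (including PMI and NITE), noncardiac MAPE and all-cause mortality will be presented as proportions". The next sentence reads "Multivariable logistic regression analyses will be performed using MACE, noncardiac MAPE or all-cause mortality as outcomes, both in-hospital events and at 6 months", and the one after it "Different combinations of elevations in biomarkers (preoperative, postoperative and change between pre- and postoperative) will be tested against these outcomes". The last bullet of 7.3 returns to MACE for the added value over the RCRI: biomarkers "will be tested to predict MACE, both in-hospital and at 6-months". That bullet does not repeat the parenthesis and names no biomarker timepoints, although objective 4 speaks of perioperative measurement.

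PMI is defined in section 1 as a troponin I elevation and is divided there into MI and NITE. Section 5.1.3 lists hsTroponin on postoperative days 1-3 among the biomarkers.

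The lists also disagree with one another. The summary's endpoint list omits stroke from MACE and defines noncardiac MAPE as "consisting of respiratory disorders (including pneumonia and respiratory failure), pulmonary embolism, sepsis" and further items. The summary objectives, 2.2 and 5.1.2 count stroke and pulmonary embolism as MACE; in 5.1.2 the latter is "Pulmonary embolism, defined as a new thrombus within the pulmonary arterial system confirmed on CTA".

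**The concern.** If the 7.3 wording governs the models, every troponin I elevation is a MACE. Postoperative troponin and its change would then partly predict themselves, and part of any odds ratio would come from the definition. For BNP, CRP, hemoglobin, creatinine, ECG and TTE, the outcome would be mostly troponin elevation, so the results would describe PMI rather than MACE.

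The parenthesis bears on objective 2a and on the MACE part of objective 3, since sections 3 and 5.3 collect 6-month events from the day of surgery and so include the in-hospital ones. It bears on objective 4 only if both the wording and postoperative values carry into the RCRI models; part of any gain in c-statistic, NRI or IDI would then be built in.

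The list discrepancy has a different reach. Moving pulmonary embolism between composites changes noncardiac MAPE, which is the outcome of objective 2b and one of the exposures compared in the primary objective.

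**Working it through.** The plan gives no MACE rate or MACE event count, so there is no figure of its own to reproduce.

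**Inputs from the documents.** PMI P = 0.11 (section 4.4). MI is about one third of PMI (section 1), so MI = 0.11/3 = 0.0367.

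**Assumed.** Other listed MACE in a share x of patients, with x = 1%, 3% or 5%, independent of troponin. Section 1 gives a rough anchor: 19% of patients have a MAPE and 19% of MAPE are cardiovascular, so 0.19 × 0.19 = 3.6%. That figure may already include MI.

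**Events**

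- MACE as in 7.3 = P + (1 − P)x. At x = 0.03: 0.11 + 0.89 × 0.03 = 0.1367, or 68 per 500.
- MACE as in 5.1.2 = MI + (1 − MI)x. At x = 0.03: 0.0367 + 0.9633 × 0.03 = 0.0656, or 33 per 500.
- NITE only = (P − MI)(1 − x). At x = 0.03: 0.0733 × 0.97 = 0.0711, or 36 per 500. This equals the difference of the two lines above, as it should.

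| Other MACE x | 7.3 MACE per 500 | 5.1.2 MACE per 500 | PMI share of 7.3 MACE | NITE-only share of 7.3 MACE |
|---|---|---|---|---|
| 1% | 59 | 23 | 93% | 61% |
| 3% | 68 | 33 | 80% | 52% |
| 3.6% | 71 | 36 | 77% | 50% |
| 5% | 77 | 42 | 71% | 45% |

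A second route counts x only in patients without troponin elevation. At x = 3.6% the troponin share is 110/146 = 75% with PMI at 11%, 150/186 = 81% at 15%, and 190/226 = 84% at 19%. With PMI at 11%, troponin elevations lose their majority only if at least 11% of all patients have a listed MACE without one.

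**Discrimination of a binary marker that carries no other information.** Let a share q be marker-positive and let the marker detect a share s of troponin I elevations. True positives are TP = sP + (q − sP)x under 7.3 and TP = sMI + (q − sMI)x under 5.1.2. For a binary marker c = (sensitivity + specificity)/2.

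Discordant case, assumed: q = 0.22, s = 0.8. At x = 0.03:

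- 7.3: TP = 0.088 + 0.132 × 0.03 = 0.0920; sensitivity = 0.0920/0.1367 = 0.673; specificity = 1 − 0.1280/0.8633 = 0.852; c = 0.76.
- 5.1.2: TP = 0.0293 + 0.1907 × 0.03 = 0.0351; sensitivity = 0.0351/0.0656 = 0.535; specificity = 1 − 0.1849/0.9344 = 0.802; c = 0.67.

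| Case | x | c under 7.3 | c under 5.1.2 |
|---|---|---|---|
| Discordant assays (q = 0.22, s = 0.8) | 1 / 3 / 5% | 0.80 / 0.76 / 0.73 | 0.74 / 0.67 / 0.63 |
| Full agreement (q = 0.11, s = 1) | 1 / 3 / 5% | 0.96 / 0.90 / 0.86 | 0.87 / 0.76 / 0.70 |

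**Check without independence.** Section 1 links PMI to arrhythmias and pulmonary embolism, so let other MACE be three times as frequent in PMI patients: rate b = x/(1 − P + 3P) without PMI and 3b with PMI. At x = 0.03, b = 0.03/1.22 = 0.0246, 7.3 MACE = 0.11 + 0.89 × 0.0246 = 0.1319, and the PMI share is 83%. Over x = 1-5% the share is 94-75%. In the discordant case c under 7.3 is 0.81-0.74, against 0.55-0.56 on MACE without MI. The result does not rest on independence.

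**The case against.** The strongest reply is that 5.1.2 is the section that defines endpoints, and that a single parenthesis in a sentence about reporting proportions should not override it. PMI already contains NITE, so the phrase is redundant and looks like a slip; it may only mean that PMI and NITE are tabulated beside MACE. This largely stands as an account of how the phrase arose, and it makes the harm conditional. It does not settle the matter. The text does not say alongside, a slip for MI and NITE would still add NITE, and the regression sentences follow directly with no pointer to 5.1.2.

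Second, full assay agreement is not what the documents lead one to expect. PMI is defined on troponin I, the batch-measured predictor is hsTroponin, and section 5.3 says the high-sensitivity assay doubles detection of MI. This stands. The full-agreement figures are an upper illustration. In the discordant case the wording adds about 0.06-0.10 to c, and that case is itself one assumed scenario, not a bound.

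Third, overlap through MI exists under 5.1.2 too. This also stands: deleting the parenthesis reduces the overlap but does not remove it.

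A reader might infer that the primary result is circular, or that the RCRI models are certain to be affected. The documents support neither. The primary outcome is WHODAS 2.0, which the parenthesis does not touch, and the RCRI bullet neither repeats the parenthesis nor says that postoperative values enter.

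**Conclusion.** The conflict in the text is certain and should be fixed; its consequence is conditional on the 7.3 wording being applied in the models. If it is, then at 11% PMI, one third of it MI, and other MACE at an assumed 1-5%, about 71-93% of MACE patients would be PMI patients and about 45-61% would have NITE only. A postoperative troponin marker with no other information would reach c of about 0.73-0.80 in the assumed discordant case, against 0.63-0.74 under 5.1.2; with full agreement, 0.86-0.96 against 0.70-0.87. Only a binary marker was modelled.

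The parenthesis leaves the primary WHODAS analysis, noncardiac MAPE and all-cause mortality unchanged. That statement does not extend to the summary's endpoint list: where pulmonary embolism is counted changes noncardiac MAPE, and with it objective 2b and one exposure in the primary objective. The size of that effect cannot be derived, because the documents give no pulmonary embolism rate.

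**What to change.** 1. In 7.3, delete the parenthesis naming PMI and NITE, state that the 5.1.2 MACE list applies in all MACE models including the RCRI models, and report PMI and NITE as separate proportions.
2. Reconcile the MACE and noncardiac MAPE lists in the summary's endpoint section with 5.1.2, in particular for stroke and pulmonary embolism.
3. When interpreting models with postoperative troponin or its change, note the remaining overlap through MI. A descriptive analysis on MACE without MI is optional. If it is done, say how fatal MI is handled, since 5.1.2 includes "Cardiovascular death, defined as death resulting from an acute myocardial infarction" among other causes.

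Cost: wording changes only; sampling and data collection stay as they are. There would be fewer MACE events than under 7.3 (about 23-42 instead of 59-77 per 500 at the assumed rates) and a less favourable figure for troponin. The optional analysis would be imprecise, with 5-25 events per 500 (500 × 1% to 500 × 5%) or 10-50 in the combined 1,000. At the low end that is too few for six RCRI predictors plus biomarkers.

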4.4 Sample size calculation

For this study, we aim to include 500 patients at the UMCU in this study. A similar study will be conducted at the University Health Network Toronto (UHNT), Toronto, Canada and they will include 500 patients with the same in- and exclusion criteria. After including all patients in both centers, we will combine the data resulting in a total study population of 1,000 patients. In a previous conducted pilot study by the UHNT (registered at ClinicalTrial.gov: NCT02146560), 300 patients undergoing major elective noncardiac surgery were included and disability was assessed by the WHODAS 2.0 after 6 months. The incidence of troponin elevation in this pilot was 14.1%. We do however expect an incidence of 11.0% as patients included in the pilot were mainly vascular patients, who are more

prone to have postoperative troponin elevations⁴. The mean WHODAS 2.0 in patients with an elevation in troponin was 29% compared to 15% in patients without troponin elevation. Based on these results, and using a level of significance of 0.05 and a power of 0.8 we expect 104 patients with troponin elevation. As the ratio between troponin elevation and no troponin elevation is $0.89/0.11 = 8$, we need to include 832 patients. We expect a dropout of 20% (based on the number of patients who did not fill out the WHODAS 2.0 after 6 months in the pilot study), leading to a final sample size of approximately 1,000 patients.

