7.2 Primary study parameter(s)

The primary outcome, postoperative WHODAS 2.0 after 6 months, will be compared among patients with and without PMI, using Student's t-test or a nonparametric Mann Whitney U test. In case of normality, the mean 6-months WHODAS 2.0 will be calculated together with the accompanying 95% confidence intervals. Otherwise, the median WHODAS 2.0 with interquartile range will be reported.

With respect to the association between the different phenotypes of PMI (i.e. myocardial infarction, NITE and MAPE) and disability, the preoperative, postoperative and the change (meaning difference between pre- and postoperative measurements) in biomarkers are of particular interest. The biomarkers will be analyzed both as continuous variables and using predefined clinical thresholds to define when the each of the biomarkers are elevated.

Combination(s) of different biomarkers and the biomarker by itself in association with postoperative WHODAS 2.0 will be performed. These combination(s) of biomarkers will be related to one of the different phenotypes of PMI. Multivariable linear regression analyses will be performed to adjust for potential confounders including age, gender, comorbidities (cardiovascular risk factors), preoperative WHODAS 2.0 score, RCRI and surgical specialty.

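### Section 7.3 names biomarkers only as elevated or not for disability-free survival and for the MACE, noncardiac MAPE and mortality association models, and leaves the Cox form unstated; the continuous form used in 7.2 should be added

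*Combined protocol and SAP*

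**What the plan says.** The biomarker form named for each outcome is as follows.

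- **WHODAS 2.0 (7.2):** both forms. "The biomarkers will be analyzed both as continuous variables and using predefined clinical thresholds to define when the each of the biomarkers are elevated".
- **Disability-free survival (7.3):** elevation. "Different combinations of elevation in biomarkers will be tested". The logistic sentence that follows concerns PMI phenotypes and covariates and names no biomarker term.
- **MACE, noncardiac MAPE and all-cause mortality (7.3, logistic; in hospital and, except for noncardiac MAPE, at 6 months):** elevation. "Different combinations of elevations in biomarkers (preoperative, postoperative and change between pre- and postoperative) will be tested against these outcomes to uncover correlations". The sentence then gives its purpose, which is to learn which disease entities go with the outcome.
- **6-month mortality (7.3):** the log-rank comparison is "between patients with and without elevation in (one or more) biomarker(s) will be compared using log-rank tests". The adjusted Cox sentence speaks of one or several biomarkers without giving a form.
- **Added value over the RCRI for MACE (7.3):** both forms. "The biomarkers will be analyzed as continuous variables and using predefined clinical thresholds to define whether that particular biomarker is elevated". The model sentence that follows nevertheless describes the added term as elevation.

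**The concern.** High-sensitivity troponin, BNP, CRP, creatinine and hemoglobin are assayed as quantities before surgery and on days 1 to 3 (5.1.3, 5.3). Cutting them treats a value just over the threshold like an extreme one, and cutting the perioperative change discards the size of the rise. The plan gives no reason for using only the cut form in these bullets.

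The rule in 7.2 cannot safely be read across. It sits under the primary parameter, and the RCRI bullet restates it for its own use.

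Secondary objectives 2 and 3 ask whether biomarkers are associated with MAPE, MACE and mortality. If risk is graded, a test on the cut scale can miss an association that the same samples would show on the continuous scale, and the null result would then be read as no association.

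**Working it through.** **The plan's own figures.** No power is stated for any biomarker analysis of these outcomes. The only calculation (4.4) is for WHODAS: "using a level of significance of 0.05 and a power of 0.8 we expect 104 patients with troponin elevation". There, 104 × 8 = 832 and 832 × 1.2 = 998, close to the stated 1,000. The 104 cannot be reproduced because no SD is given: the 14-point difference (29% versus 15%) with groups of 104 and 832 would imply an SD of 14 / (2.802 × √(1/104 + 1/832)) ≈ 48. That calculation is a separate matter. It is used here only for the 0.05 level, N and the expected share with elevated troponin: "We do however expect an incidence of 11.0% as patients included in the pilot were mainly vascular patients".

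**Inputs**

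- From the documents: level 0.05 (taken as two-sided), N = 1,000, 20% dropout (so 800 with 6-month WHODAS), and 11% with elevated troponin.
- Assumed: elevated shares of 25% and 50% for other markers, a normal biomarker after transformation, log-odds linear in it, and 80% power on the continuous scale.

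**Efficiency of a cut.** For a standard normal marker cut at c with share p above it, E = φ(c)² / (p(1 − p)). The continuous test has noncentrality 1.960 + 0.842 = 2.802. After the cut, power = Φ(2.802 × √E − 1.960).

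| Share elevated | E | Noncentrality after cut | Power after cut |
|---|---|---|---|
| 11% | 0.188² / 0.0979 = 0.361 | 1.683 | 39% |
| 25% | 0.318² / 0.1875 = 0.539 | 2.056 | 54% |
| 50% | 0.399² / 0.25 = 0.637 | 2.235 | 61% |

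In terms of information, 1,000 patients then count as about 360, 540 or 640. Starting from 90% power, the cut leaves 50%, 66% and 73%. Starting from 50%, it leaves 22%, 30% and 35%.

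**Simulation under the same log-linear assumption** (logistic model, Wald test, 3,000 replicates). Event rates and odds ratios are assumed. The 15.4% is 19% × (1 − 0.19), from the external cohort cited in section 1.

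| Scenario | Continuous | Cut at 11% / 25% / 50% elevated |
|---|---|---|
| N = 1,000, 15.4% events, OR 1.28 per SD | 80% | 45% / 58% / 61% |
| N = 1,000, 5% events, OR 1.5 per SD | 79% | 49% / 58% / 58% |
| N = 800, 25% events, OR 1.26 per SD | 80% | 45% / 58% / 60% |

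**When the direction changes**

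- *Step in risk at the threshold.* With a step at the 11% cut and OR 1.9, power is 37% continuous and 72% cut. Across other simulated step scenarios (600 runs each) the cut gained about 12 to 37 points.
- *Skewed values left untransformed.* With log-linear risk but raw lognormal values (log-scale SD 1.2, assumed), the continuous test had 30% to 50% power against 41% to 61% for the cut. The cut did not win in every case: with 25% events and 11% elevated, the raw continuous test had 48% against 41%.

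**The case against.** Four points on the other side carry weight.

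- **The word elevation may be loose.** The RCRI bullet states that both forms are used and then describes its models as adding elevation. The authors may therefore intend continuous analysis in the other bullets too. This stands as doubt about intent, but an analyst following 7.3 literally would fit only the cut form.
- **Thresholds serve a stated aim.** The logistic bullet looks for patterns of elevated markers that point to a disease entity, and continuous main effects alone do not identify such patterns. This stands, and it argues for keeping the thresholds rather than demoting them.
- **The sizes are assumed.** The documents give no effect per SD, no elevated share for BNP, CRP, hemoglobin or creatinine, and no planning rate for mortality or disability-free survival. The 15.4% comes from another cohort, whereas this protocol's noncardiac composite also counts reoperation and unplanned ICU or medium care admission (5.1.2). The simulations are unadjusted, while the planned models are adjusted. This stands: the loss is conditional.
- **The analyses are secondary, with no power target.** This stands and limits the weight of the point.

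A reader might also infer that the plan protects MACE by analysing it continuously. It does so only for added value over the RCRI (objective 4). MACE as an association outcome (objectives 2a and 3) is in the same elevation-only sentence as noncardiac MAPE and mortality. Nor is 6-month mortality analysed only on the cut scale: the logistic and log-rank analyses are worded that way, but the Cox form is open.

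**Conclusion.** The point holds as a cheap improvement. As worded, 7.3 names only elevated or not for disability-free survival (objective 1) and for the logistic association models of MACE, noncardiac MAPE and all-cause mortality (objectives 2 and 3). It does the same for the log-rank groups and leaves the Cox model unspecified.

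Under log-linear risk, suitable transformation and 80% power on the continuous scale, the cut lowers power to about 39%, 54% or 61% at 11%, 25% or 50% elevated. Only the 11% comes from the plan, and only for troponin.

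A reader might infer a fixed power loss for these objectives. The documents do not support one: the loss depends on the unknown shape of risk, the effect size and the share elevated. It reverses for a step at the cut and can reverse for untransformed skewed values. Naming the continuous form without a transformation would therefore not secure the gain.

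**What to change.** In section 7.3, extend the 7.2 rule to every outcome: disability-free survival, MACE as an association outcome, noncardiac MAPE and all-cause mortality, in both logistic and Cox models. State that each blood biomarker and its change from before to after surgery is also analysed as a continuous term, log-transformed where skewed, with a linearity check, or a spline where event numbers allow. Make the model sentence in the RCRI bullet match the both-forms sentence before it. Keep the threshold combinations alongside, for the aim of identifying disease entities.

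The cost is a wording change, a little more analysis and a second set of estimates to report. It needs no extra patients, samples or assays. Section 5.3 has the stored samples assayed in one batch after the last patient's discharge, so wording settled before then would precede those results.
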